As secondary objectives of the study, the efficacy of lithium will be evaluated for the prevention of subtypes of suicidal self-directed violence, for all suicidal self-directed violence events (even after the first recurrence), for the prevention of repeated events in subgroups as well as the entire sample, and to identify potential mediators.

The tertiary objective of the study is to extend the follow up period using electronically available data to describe patterns of lithium use following active participation in the study participants, as well as to evaluate rates and determinants of suicide reattempts and all cause mortality over a longer follow up period.

The study will enroll and randomize 1,862 patients to receive either lithium or placebo with enhanced usual care. The study is projected to run a total of 4.5 years with 3 years of recruitment, 1 year of follow-up on lithium or placebo, and time for start-up and closeout as indicated in the study budget. We expect to enroll, on average, 65 patients per site at 29 VA medical centers.

V. STUDY POPULATION

Inclusion Criteria

Admission of patients to CSP590 will require that:

1. They have survived an episode of suicidal self-directed violence (including suicide attempts and interrupted attempts; see below) that occurred within six months of initial consent to the study, or they were admitted to a mental health inpatient unit specifically to prevent suicide within six months of initial consent to the study.
2. They have a diagnosis of an affective disorder meeting DSM-IV-TR (2000) criteria for Bipolar I Disorder, Bipolar II Disorder, or current or recurrent Major Depressive Disorder. Meeting the diagnosis for a current Major Depressive Disorder requires the presence of a Major Depressive Episode (see below).
3. They are able and willing to identify one or more family members, friends, or other contacts and give permission for both clinical providers and the Research Team to contact them if the patient cannot be reached.
4. They are able to provide informed consent
5. There is concurrence from the patient's mental health provider about inclusion/exclusion criteria and confirmation of the providers' willingness to work with the research team in managing the patient during the course of the study (see below). The provider responsible for the patient's general medical care has been made aware of the participation

Rationale:

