 - 6. individuals with and without trait aggression
 - 7. subjects who have vs. have not received evidence based psychotherapies
- (c) To explore the effect of lithium augmentation of enhanced suicide prevention management on total occurrence of all event types combined and individual event type as follows:
 - 1. all suicide attempts
 - 2. all suicide attempts plus interrupted attempts
 - 3. all hospitalizations for the prevention of suicide
 - 4. all self-directed violence
 - 5. all emergency department visits
- (d) To explore longitudinally the effect of lithium augmentation of enhanced suicide prevention management on symptoms of bipolar disorder and depression and suicidal ideation
- (e) To explore mediators of the effect of lithium augmentation on prevention of episodes of suicidal self-directed violence, specifically improved control of symptoms and lithium plasma levels

Secondary objective (a) will use a time to event, survival analysis to determine whether there is a treatment difference in event rates for each of the defined endpoints. The null hypothesis for each endpoint is that the two treatment groups do not differ in their hazard rates. The alternative hypothesis is that the intervention group on lithium has a lower hazard rate than the placebo group. The log-rank test and Cox proportional hazards models will be used.

For secondary objective (b), the null hypothesis for each of the factors is that treatment effect does not differ over levels of the factor. The alternative hypothesis is that there is differential treatment effect over levels of the factor. Effect modification will be tested through the use of interaction terms in the Cox proportional hazards regression model with main effects of treatment and factor and an interaction of the two. A forest plot will be used to display the results.

Secondary objective (c) will be evaluated using Poisson regression to model for grand total numbers of events and for total number of each event type controlling for follow up time. The null hypothesis for this objective will be that total event rates do not differ by treatment assignment. The alternative hypothesis is that there is a difference in total event rates across treatment groups.

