Secondary objective (d) will be evaluated using mixed effect models allowing for random variation in symptoms of bipolar disorder and depression at baseline. The null hypothesis for this objective will be that change in symptoms and suicidal ideation in the lithium group is similar to that of the placebo group. The alternative hypothesis is that there is a difference in change across treatment groups over time.

Secondary objective (e) will be evaluated by regression analysis method comparing regression coefficients for treatment effect in the models with and without the mediator (Sobel, 1982), as well as by bootstrapping methods, (MacKinnon et al., 2002; Preacher & Hayes, 2008; Tein & MacKinnon, 2003).

Tertiary Data Analysis Plan

These exploratory objectives (explained further in Section XIV) are to analyze electronically available data over the extended follow up period to:

- (a) describe pattern of Lithium use following active participation in the study participants,
- (b) evaluate suicide reattempt and all cause mortality over a longer follow up period, both for the study population and patients who were evaluated for enrollment under HIPAA waiver (“pre-screen” population), and
- (c) evaluate all cause mortality over a longer follow up period.

Tertiary objective (a) will be evaluated by descriptive analysis on duration of lithium use, and by regression modeling to determine factors associated with any lithium use within one month following active study participation.

Tertiary objectives (b) and (c) will be evaluated using time to event survival analysis and Cox regression modeling to determine correlates of suicide reattempts and all cause mortality in the study population.

Data Repository

The Boston CSP Coordinating Center will create a data repository under the Boston IRB oversight for research purposes. Data will be housed at the Boston Cooperative Studies Program Coordinating Center and will be made available to appropriately credentialed researchers conducting studies related to suicide, lithium, or other health questions, in accordance with the Repository Protocol and relevant SOPs.

VIII. POTENTIAL PITFALLS OF THE PROPOSED DESIGN AND ALTERNATIVE DESIGN CONSIDERATIONS

Potential pitfalls of the trial include the threats to internal and external validity inherent in any clinical trial and those of particular concern to this study question.

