5.2. Secondary Endpoints

There are multiple secondary endpoints being considered for the study where endpoint events for secondary objectives #1, 2, and 5 will be assessed as time to event outcomes, endpoint events for secondary objective # 3 will be assessed as count data, and endpoint events for Secondary Objective #4 will be evaluated as a binary outcome.

For Secondary Objective #1, Time from randomization to death from any cause will be analyzed. Additionally, self-directed violence as described in section 4.2 will be classified further as either impulsive or non-impulsive attempt based on Beck Suicide Intent Scale, (Question#15 on CRF-Form S8), and will be analyzed separately. Lastly, non-suicidal self-directed violence behavior defined as the primary endpoint without the death from suicide will be considered as a separate outcome.

For Secondary Objective #2 which evaluates efficacy in different subgroups, the primary endpoint as described in section 4.2 will be analyzed.

The endpoint for Secondary Objective #3 considers all components of self-directed violence as described in section 4.2. Therefore, a combined total of all episodes of all components of the primary outcome will be an endpoint, and total counts of each component, in addition to all emergency department visits will be separate endpoints.

For Secondary Objective #4, dependent variables being considered longitudinally include (1) presence or absence of symptoms, and (2) presence or absence of suicidal ideation. Presence or absence of symptoms will be derived by the Internal State Scale (CRF-Form B8), and presence or absence of suicidal ideation will be derived from the Columbia Follow Up Questionnaire (CRF-Form B6).

Lastly, for Secondary Objective #5, the endpoint event will be the same as the primary endpoint described in section 4.2.

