5.3. Statistical Methods for Secondary Analyses

Secondary objective#1 will use a time to event, survival analysis to determine whether there is a treatment difference in event rates for each of the defined endpoints. The null hypothesis for each endpoint is that the two treatment groups do not differ in their hazard

rates. The alternative hypothesis is that the intervention group on lithium has a lower hazard rate than the placebo group. As with the primary analysis, log-rank test and Cox proportional hazards models will be used.

For secondary objective#2, the null hypothesis for each of the factors is that treatment effect does not differ over levels of the factor. The alternative hypothesis is that there is differential treatment effect over levels of the factor. Effect modification will be evaluated through regression methods. Cox proportional hazards regression model will include the treatment term, a term for the target factor, and the interaction term of the two. If the null hypothesis is rejected at $p=0.05$ level, i.e., the interaction term in the model is statistically significant, separate regression models will be refitted for each level of the factor. A forest plot will be used to display the results.

For secondary objective#3, the null hypothesis is that total event rates do not differ by treatment assignment, and the alternative hypothesis is that there is a difference in total event rates across treatment groups. We will use Generalize Linear Models (glm), namely Poisson regression, to model cumulative total of endpoint events with an offset for follow up time.

For secondary objective#4, the null hypothesis is that change in symptoms and suicidal ideation in the lithium group is similar to that of the placebo group. The alternative hypothesis is that there is a difference in change across treatment groups over time. We will use Generalize Linear Models (glm), namely Logistic regression, to model presence or absence of symptoms and suicidal ideation at each follow up visit, while allowing for random effects of variation in symptoms of bipolar disorder and depression at baseline.

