Secondary objective#5 will be evaluated by Cox Proportional Hazard regression analysis method comparing regression coefficients for treatment effect in the models with and without the mediator (Sobel, 1982). Additionally, we will explore bootstrapping methods to evaluate mediators as described in MacKinnon et al.(2002), Preacher & Hayes (2008), and MacKinnon (2003).

6. Analysis Plan for Tertiary Objectives

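### The symptom-mediation analysis leaves baseline symptom severity out of both Cox models, so a symptom score with no causal role can appear to mediate lithium's effect

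*Protocol*

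**What the plan says.** Protocol section VII (Secondary Data Analysis Plan), objective (e), names the candidate mediators: "specifically improved control of symptoms and lithium plasma levels". The method is "comparing regression coefficients for treatment effect in the models with and without the mediator", by the Sobel approach, with bootstrapping in addition. The Protocol leaves the type of regression open. SAP 5.3 settles it: "Secondary objective#5 will be evaluated by Cox Proportional Hazard regression analysis method". SAP 5.2 adds for this objective only that "the endpoint event will be the same as the primary endpoint described in section 4.2".

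For this objective, neither document states which symptom score is meant, at which visit, how it is coded, whether the baseline score is a covariate, or that the score must precede the event. The nearest clauses belong elsewhere:

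- SAP 5.2, for Objective 4: "Presence or absence of symptoms will be derived by the Internal State Scale (CRF-Form B8". This is a binary measure, and nothing extends it to Objective 5.
- SAP 5.3, for Objective 4: the model is fitted "allowing for random effects of variation in symptoms of bipolar disorder and depression at baseline". This allowance is not carried into Objective 5.
- SAP 4.4: covariates are added to the primary Cox model, and only those that differ between the arms.
- Protocol Table 6: PHQ-9 and ISS are recorded at baseline and repeatedly through follow-up.
- Protocol section IV: lithium is to be evaluated "for all suicidal self-directed violence events (even after the first recurrence". Participants are therefore still scored after a first event.
- SAP 5.1: the secondary analyses are exploratory and not powered for formal tests.

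**The concern.** This point is about the symptom mediator, not plasma level. Randomisation protects the path from treatment to symptoms. It does not protect the path from symptoms to events. A participant who is more severely ill at baseline is likely to have higher scores later and a higher event rate. If baseline severity is in neither model, the later score picks up its prognostic value. If lithium also lowers the score, the treatment coefficient shrinks when the score is added, and this looks like mediation. Perfect balance between the arms does not prevent it, so SAP 4.4 would not help even if it applied. The bootstrap resamples the same biased contrast.

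The question matters to the trial's rationale. Protocol section I argues that any effect on suicide may not run through control of affective symptoms. A spurious mediation result would count against that model when it is true. Section XX lists a publication on mediators.

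**Working it through.** **1. Trial size (the plan's own figure).** The documents give no figure for the mediation analysis, so the check starts from the primary design: 745 evaluable per arm, with event rates of 15% and 9.45%.

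- Events: 745 × (0.15 + 0.0945) = 182.15, against 182 stated.
- HR: ln(0.9055) / ln(0.85) = 0.611, against 0.61 stated.
- Log-rank power: Φ(√(182/4) × |ln 0.61| − 1.96) = Φ(3.334 − 1.960) = 0.915; at two-sided 0.048 it is 0.913. Two-proportion power is 0.906 and 0.903.

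The stated 90% reproduces, so these values are used below.

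**2. Size of the bias.** Let B be baseline severity in SD units. Let the follow-up score be M = ρB + aT + noise, and the log hazard be γB + ln(0.61)T. M has no effect on the event, so true mediation is zero. With B omitted, the Cox coefficient of M is about b = ργ instead of 0. The Sobel statistic is z = ab / √(a²·se_b² + b²·se_a²). The apparent mediated share is (c − c′)/c, where c and c′ are the treatment coefficients without and with M.

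The values of ρ, γ and a are assumptions. There were 1,000 trials per row, 745 per arm and no dropout. A trial counts as significant if |z| > 1.96 in the direction of benefit through lower symptoms.

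| ρ | γ (HR per SD) | symptom drop | ργ | simulated b | significant, as planned | spurious share | significant, baseline in both models |
|---|---|---|---|---|---|---|---|
| 0 (control) | 0.4 (1.49) | 0.2 SD | 0 | 0.003 | 0.8% | 0.1% | 0.8% |
| 0.3 | 0.2 (1.22) | 0.2 SD | 0.06 | 0.059 | 6.0% | 2.3% | 1.6% |
| 0.5 | 0.4 (1.49) | 0.1 SD | 0.20 | 0.199 | 17.6% | 3.8% | 0.2% |
| 0.5 | 0.4 (1.49) | 0.2 SD | 0.20 | 0.196 | 59.5% | 7.6% | 1.1% |
| 0.6 | 0.5 (1.65) | 0.3 SD | 0.30 | 0.297 | 97.1% | 18.0% | 1.4% |

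Worked share, fourth row: (0.498 − 0.460)/0.498 = 7.6%. With the baseline score in both models the share is about 0% in every row. Joint significance of both paths, a rough stand-in for the bootstrap, gave 11% to 98% in the four confounded rows.

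**3. With 40% uniform dropout** (400 to 600 trials per setting):

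- Correlation 0.6, HR 1.5 per SD, drop 0.2 SD: 64% to 66% significant, share about +9%. If change from baseline is the mediator, 47% to 48% and about −8% to −9%, so the sign depends on the coding.
- Drop 0.2 SD with weaker confounding: 22% to 25% (0.5, HR 1.3), 16% (0.4, HR 1.3), 7% to 8% (0.3, HR 1.2).
- Drop 0.1 SD: 20% (0.6, HR 1.5), 5.5% (0.5, HR 1.3), 2.5% (0.4, HR 1.3), 1% (0.3, HR 1.2).
- No lithium effect on symptoms: 0.5% to 1.5%.
- Mediator split at the median, in the 0.6 / 1.5 / 0.2 SD setting: 32%, share 6%.

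**4. If scores recorded after a first event were used** (conditional; the plan does not say so). Suppose such scores run 0.5 SD higher and lithium lowers scores by 0.2 SD. Without baseline confounding, 99% of trials are significant, with a 20% share. With ρ = 0.5 and γ = 0.4 added:

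| Analysis | significant | share |
|---|---|---|
| As planned | 99% | 28% |
| Baseline score only | 99.7% | 26% |
| 3-month landmark only | 44% | 8% |
| Both | 1.4% | about 0% |

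If lithium does not move symptoms and post-event scores are the only fault, the rate is 6% for a 0.5 SD shift and 14% for a 1 SD shift.

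**The case against.** The strongest reply is that the plan is brief, not wrong, and that a sensible analyst would fill the gaps. Several parts of this stand.

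- **Post-event scores.** A reader might infer that such scores will enter the model and quote the 97% to 99% figures. The documents do not support that. Objective 5 uses the primary endpoint, and primary follow-up time stops at the first event (Protocol section VII; SAP 4.3). A lagged or time-varying score is not excluded. What stands is that no rule keeps later scores out.
- **Assumed inputs.** Correlation, prognostic strength and lithium's effect on symptoms are all supplied here. Weak inputs give rates near or below nominal.
- **The measure.** The SAP's only operational definition of symptoms is binary, and a dichotomised score roughly halves the base-case rate, from about 65% to 32%.
- **Importance.** A spurious share of a few percent is not a claim that lithium works through symptoms. A reader might also take this to be the trial's only analysis of mechanism. It is not: the impulsive versus non-impulsive comparisons (Protocol section VI, Other Outcomes; objectives (a) and (b)) also bear on it.

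The missing baseline score does not yield to these points. Followed as written, the two models differ only by the mediator, and no other clause supplies the covariate. An exploratory label excuses low power. It does not excuse an avoidable bias.

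**Conclusion.** The point holds for the baseline score. Under moderate assumed inputs the planned comparison declares mediation falsely in roughly 6% to 65% of trials. Under strong inputs the rate reaches 97%, and it is about 1% if lithium leaves symptoms unchanged. The spurious share is about 2% to 18%. With the baseline score in both models, false positives fall to 0% to 4% and the share to about zero, provided the symptom scores precede the event.

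The absence of a pre-event rule is a second, conditional gap: serious if post-event scores were used, but not something the plan prescribes. It would be wrong to conclude that the mediation result is bound to be false or that the primary comparison is affected. This is one exploratory secondary analysis, worth correcting before it is run.

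**What to change.** In SAP 5.3 (Objective 5) and Protocol objective (e):

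1. Name the symptom measure (PHQ-9, ISS or both), its coding and its visits, and reconcile this with the binary ISS definition that SAP 5.2 gives for Objective 4.
2. Put the baseline score of the same scale in both Cox models and in the mediator model.
3. Fit both Cox models on the same participants and the same risk time. State how time before the first follow-up score is handled.
4. Use only scores dated before the event, preferably as a lagged time-varying covariate. A landmark is an alternative.
5. Keep the bootstrap interval, and state that unmeasured symptom-event confounding remains.

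The cost is SAP wording and a few lines of code, since baseline and follow-up scores are already collected. The landmark option costs more. At month 3 it drops about 31% of observed events in the simulation with dropout (0.31 × 182 ≈ 56 if applied to the planned total). It also conditions on being event-free, so the comparison is no longer fully randomised, and it falls as the titration period in SAP 3.2 ends. If it is chosen, the report should say that it covers later events only.
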